15.4 Quality Assurance Monitoring

In accordance with federal regulations, the study sponsor is responsible for ensuring proper monitoring of an investigation and ensuring that the investigation is conducted in accordance with the protocol. Qualified monitors will oversee aspects of site conformity to make certain the site staff is operating within the confines of the protocol, and in accordance with GCP. This includes but is not limited to protocol compliance, documentation auditing, and ensuring the informed consent process is being correctly followed and documented. Non-conformity with protocol and federal regulations will be reported as a protocol deviation and submitted to the study sponsor and study IRB of record (as applicable) for further review.

15.5 Participant and Data Confidentiality

Participant confidentiality and privacy are strictly held in trust by the participating investigators, their staff, the safety and oversight monitor(s), and the sponsor(s) and funding agency, and will be maintained in accordance with all applicable federal regulations and/or state/Commonwealth law and regulations. This confidentiality is extended to the data being collected as part of this study. Data that could be used to identify a specific study participant will be held in strict confidence within the research team. No personally-identifiable information from the study will be

released to any unauthorized third party without prior written approval of the sponsor/funding agency or the participant.

All research activities will be conducted in as private a setting as possible.

The study monitor, other authorized representatives of the sponsor or funding agency, representatives of the Institutional Review Board (IRB), regulatory agencies or representatives from companies or organizations supplying the product, may inspect all documents and records required to be maintained by the investigator, including but not limited to, medical records (office, clinic, or hospital) and pharmacy records for the participants in this study. The clinical study site will permit access to such records.

Participant records will be held confidential by the use of study codes for identifying participants on CRFs, secure storage of any documents that have participant identifiers, and secure computing procedures for entering and transferring electronic data. The study participant's contact information will be securely stored for internal use during the study. At the end of the study, all records will continue to be kept in a secure location for as long a period as denoted in Section 15.11.

By signing the protocol signature page, the investigator affirms that information furnished to the investigator by NIDA will be maintained in confidence and such information will be divulged to the IRB/Privacy Board, Ethical Review Committee, or similar expert committee; affiliated institution; and employees only under an appropriate understanding of confidentiality with such board or committee, affiliated institution and employees.

15.5.1 Certificate of Confidentiality

To further protect the privacy of study participants, the Secretary, Health and Human Services (HHS), has issued a Certificate of Confidentiality (CoC) to all researchers engaged in biomedical, behavioral, clinical or other human subjects research funded wholly or in part by the federal government. Recipients of NIH funding for human subjects research are required to protect identifiable research information from forced disclosure per the terms of the NIH Policy (see <https://humansubjects.nih.gov/coc/index>). This protects participants from disclosure of sensitive information (e.g., drug use). It is the NIH policy that investigators and others who have access to research records will not disclose identifying information except when the participant consents or in certain instances when federal, state, or local law or regulation requires disclosure. NIH expects investigators to inform research participants of the protections and the limits to protections provided by a Certificate issued by this Policy.

15.5.2 Health Insurance Portability and Accountability Act (HIPAA)

The study site may be required by their institutions to obtain authorization from participants for use of protected health information. The site will be responsible for communicating with Kaiser IRB and obtaining the appropriate approvals or waivers to be in regulatory compliance. Releases of participant identifying information that are permitted by the HIPAA regulations, but which are prohibited by other applicable federal regulations and/or state/Commonwealth law and regulation, are prohibited.

15.6 Investigator Assurances

The site must have on file a Federalwide Assurance (FWA) with the HHS Office for Human Research Protection setting forth the commitment of the organization to establish appropriate policies and procedures for the protection of human research subjects in alignment with 45 CFR

46, Subpart A, with documentation sent to NIDA or its designee. Research covered by these regulations cannot proceed in any manner prior to NIDA receipt of certification that the research has been reviewed and approved by the IRB provided for in the assurance (45 CFR 46.103). Prior to initiating the study, the principal investigator at the study site will sign a protocol signature page and investigator agreement, providing assurances that the study will be performed according to the standards stipulated therein.

15.6.1 Financial Disclosure/Conflict of Interest

All investigators will comply with the requirements of 42 CFR Part 50, Subpart F to ensure that the design, conduct, and reporting of the research will not be biased by any conflicting financial interest. Everyone with decision-making responsibilities regarding the protocol will confirm to the sponsor annually that they have met their institutional financial disclosure requirements.

15.7 Clinical Monitoring

Qualified node personnel (Node QA monitors) or another designated party will provide site management for each site during the trial. Node QA staff or other designated party(ies) will audit source documentation, including electronic case report forms (eCRFs), informed consent forms and HIPAA forms. Node QA monitors will examine whether study procedures are conducted appropriately, and that the study data are generated, documented and reported in compliance with the protocol, GCP, and applicable regulations. This will take place as specified by the local protocol team, node PI(s) or Lead Node and will occur as often as needed to help prevent, detect, and correct problems at the study site. Node QA personnel will verify that study procedures are properly followed and that site personnel are trained and able to conduct the protocol appropriately. If the node personnel's review of study documentation indicates that additional training of site study personnel is needed, node QA personnel will undertake or arrange for that training. Reports will be prepared following the site visit (may be conducted remotely as appropriate) and sent to the Lead Team, Node Principal Investigator(s), and site Principal Investigator. Details of the node QA, and data monitoring are found in Module 10 of the study Manual of Operating Procedures.

15.8 Inclusion of Women and Minorities

The study site will aim and take steps to enroll a diverse study population. We are targeting approximately 50% female and 40% minority. If difficulty is encountered in recruiting an adequate number of women and/or minorities, the difficulties involved in recruitment will be discussed in national conference calls and/or face-to-face meetings, encouraging such strategies as linkages with medical sites and or treatment programs that serve a large number of women and/or minorities, advertising in newspapers or radio stations with a high female/minority readership/listening audience, etc.

15.9 Prisoner Certification

As per 45 CFR 46 Subpart C, there are additional protections pertaining to prisoners as study participants. A prisoner is defined as any individual involuntarily confined or detained in a penal institution. The term is intended to encompass individuals sentenced to such an institution under a criminal or civil statute, individuals detained in other facilities by virtue of statutes or commitment procedures which provide alternatives to criminal prosecution or incarceration in a penal institution, and individuals detained pending arraignment, trial, or sentencing.

If a participant in the study becomes incarcerated or otherwise meets the 45 CFR 46 Part C definition of a prisoner during the course of the study, and the relevant research proposal was not reviewed and approved by the Kaiser IRB in accordance with the requirements for research

involving prisoners under Subpart C of 45 CFR 46, the investigator must promptly notify the Kaiser IRB. All research interactions and interventions with, and obtaining identifiable private information about, the participant must be suspended immediately.

15.10 Regulatory Files

The regulatory files will contain all required regulatory documents, study-specific documents, and important communications. Regulatory files will be checked at the participating site for regulatory document compliance prior to study initiation, throughout the study, as well as at study closure.

15.11 Records Retention and Requirements

Research records for all study participants (e.g., electronic case report forms, source documents, signed consent forms, and regulatory files) are to be maintained by the investigator in a secure location for a minimum of 3 years after the study is completed and closed. These records are also to be maintained in compliance with IRB, state and federal requirements, whichever is longest. The Sponsor and Lead Investigator must be notified in writing and acknowledgment from these parties must be received by the site prior to the destruction or relocation of research records.

15.12 Reporting to Sponsor

The Site Principal Investigator agrees to submit accurate, complete, legible and timely reports to the Sponsor, as required. These include, but are not limited to, reports of any changes that significantly affect the conduct or outcome of the trial or increase risk to study participants. Safety reporting will occur as previously described. At the completion of the trial, the Lead Investigator will provide a final report to the Sponsor.

15.13 Audits

The Sponsor has an obligation to ensure that this trial is conducted according to good clinical research practice guidelines and may perform quality assurance audits for protocol compliance. The Lead Investigators and authorized staff from the Health Systems and Northeast Nodes; the National Institute on Drug Abuse Clinical Trials Network (NIDA CTN, the study sponsor); NIDA's contracted agents, monitors or auditors; and other agencies such as the Department of Health and Human Services (HHS), the Office for Human Research Protection (OHRP) and the Institutional Review Board of record may inspect research records for verification of data, compliance with federal guidelines on human participant research, and to assess participant safety.

15.14 Study Documentation

The participating site will maintain appropriate study documentation (including medical and research records) for this trial, in compliance with ICH E6 R2 and regulatory and institutional requirements for the protection of confidentiality of participants. Study documentation includes all case report forms, workbooks, source documents, monitoring logs and appointment schedules, sponsor-investigator correspondence, and signed protocol and amendments, Ethics Review Committee or Institutional Review Board correspondence and approved consent form and signed participant consent forms. As part of participating in a NIDA-sponsored study, the site will permit authorized representatives from NIDA and regulatory agencies to examine (and when permitted by law, to copy) clinical records for the purposes of quality assurance reviews, audits, and evaluation of the study safety, progress, and data validity.

Source documents include all recordings of observations or notations of clinical activities and any reports and records necessary for the evaluation and reconstruction of the clinical research study. Whenever possible, the original recording of an observation should be retained as the source

document; however, a photocopy is acceptable provided that it is a clear, legible, and exact duplication of the original document.

15.15 Protocol Deviations

This protocol defines a protocol deviation as any noncompliance with the clinical trial protocol. The noncompliance may be either on the part of the participant, the investigator, or the study site staff. As a result of deviations, corrective actions will be developed by the site and implemented promptly.

These practices are consistent with ICH GCP:

- Section 4.5 Compliance with Protocol, subsections 4.5.1, 4.5.2, and 4.5.3
- Section 5.1 Quality Assurance and Quality Control, subsection 5.1.1
- Section 5.20 Noncompliance, subsections 5.20.1, and 5.20.2.

Any departure from procedures and requirements outlined in the protocol will be classified as either a major or minor protocol deviation. The difference between a major and minor protocol deviation has to do with the seriousness of the event and the corrective action required. A minor protocol deviation is considered an action (or inaction) that by itself is not likely to affect the scientific soundness of the investigation or seriously affect the safety, rights, or welfare of a study participant. Major protocol deviations are departures that may compromise the participant safety, participant rights, inclusion/exclusion criteria or the integrity of study data and could be cause for corrective actions if not rectified or prevented from re-occurrence. The site will be responsible for developing corrective action plans for both major and minor deviations as appropriate. Those corrective action plans may be reviewed/approved by the Lead Node and Kaiser IRB as needed. All protocol deviations will be monitored at the site for (1) significance, (2) frequency, and (3) impact on the study objectives, to ensure that site performance does not compromise the integrity of the trial.

All protocol deviations will be recorded. The Lead Investigators must be contacted immediately if an unqualified or ineligible participant is randomized into the study.

Additionally, the site is responsible for reviewing the IRB of record's definition of a protocol deviation or violation and understanding which events need to be reported. The site must recognize that the CTN and IRB definition of a reportable event may differ and act accordingly in following all reporting requirements for both entities.

15.16 Safety Monitoring

The Lead Investigators (LI) may appoint a Study Clinician (PhD, PsyD) for this study, who will review or provide consultation for each reportable safety event as needed. These reviews will include an assessment of the possible relatedness of the event to the study intervention or other study procedures. The Study Clinician will also provide advice for decisions to exclude, refer, or withdraw participants as required. The Lead Investigators, along with input from the Study Clinicians, will determine which safety events require expedited reporting to NIDA and regulatory authorities. All events that are serious, related and unexpected, or that place subjects at greater risk of harm will be promptly reported to Kaiser IRB (IRB of Record), as outlined in KPNC IRB guidance (policy # N-CRSP HRP 071). The study staff will be trained to monitor for and report Safety Events. See local SOP safety plan for more details.

15.16.1 Data and Safety Monitoring Board (DSMB)

As this is a minimal risk study and no safety analysis will be performed (and no events are anticipated), an independent CTN DSMB will not be convened for this study. Instead, a Protocol Review Board (PRB) approved the protocol prior to implementation (January 21, 2020). As no data are being collected by the Data and Statistics Center (DSC), no annual review of accumulating data will occur. In the unlikely event that a safety issue arises, the safety events that are specified for reporting to Kaiser IRB will be reported following KPNC IRB's reporting policies.

15.16.2 Safety Monitor/Medical Monitor

Detailed Safety Monitoring will not occur via the Lead Node, due to the minimal risk nature of this study. Kaiser IRB will be responsible for reviewing all safety events reported, should there be any. All safety events that occur will be reviewed by the study team on an approximately weekly basis as part of the study operations meeting to observe trends or unusual events. Although not anticipated, if a death occurs it will be reviewed immediately. Procedures will be developed to identify notification paths to the Lead Investigators, sponsor, and all study team members. Safety events will be reported to Kaiser IRB in accordance with their reporting policies.

The Lead Investigators will in turn report safety events to the sponsor on an as needed basis (at least annually).

15.16.3 Safety Events

Standard definitions for safety events, their identification, and relationship to study and processing are described in Appendix A.

Safety events may be elicited at baseline or spontaneously reported by the study participants at any time during participation in the study.

We will only collect safety events related to suicidal ideation and death.

The Study Clinician will review each safety event as it occurs, and details will be recorded in a secure database. Safety events requiring reporting to the Kaiser IRB will be completed in accordance with Kaiser IRB's policies and procedures. Any death occurring during the study or comes to the attention of the study staff during the protocol-defined follow-up period will be reviewed with the Study Clinician and Principal Investigator(s) and will be reported to the Kaiser IRB promptly if unanticipated and possibly related to the study or otherwise at time of annual review (See Appendix A for more details).

The NIDA Program Officer must be informed of any death occurring during the study or comes to the attention of the study staff during the protocol-defined follow-up period. This report is made to NIDA regardless of whether the death was study related or unanticipated.

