20.0 APPENDIX A: SAFETY EVENT REPORTING AND PROCEDURES

The site's Principal Investigator is responsible for study oversight, including ensuring human research subject protection by designating appropriately qualified and trained study personnel to assess, report, and monitor adverse events.

Definition of Safety Events

This is a minimal risk study; therefore, no causally related Adverse Events (AE) or Severe Adverse Events (SAE) are anticipated and will not be captured. For the purposes of this protocol, safety reporting will be limited to reporting suicidal ideation and deaths only. These safety events will be captured on a Safety Event Log. The sites must follow local standard operating procedures for managing any medical or psychiatric emergencies.

As hospitalizations and overdoses of participants will be collected as data in this study, these are not considered safety events and will not be tracked on the Safety Event Log. In the event that a participant death is reported, the local team will report this to the KPNC IRB and to the study sponsor following the guidelines set forth (see the study Manual of Operating Procedures for more details).

Study staff will be trained to monitor and report all safety events on the Safety Event Log. The Log will be sent to the Lead Project Manager at least weekly, or stored on the shared drive to which all applicable study team members have access. If applicable, the Study Clinician and Lead Team will determine which safety events require reporting to KPNC IRB, NIDA CCTN and any other relevant regulatory authorities.

The study is a feasibility study, which involves three phone interviews (two baseline and one 12-week post-EMA start follow-up), and collection of active and passive digital health data (EMA, smartphone and smartwatch sensor data, and EHR and medical claims data). This study is not a clinical trial. Therefore, study safety events are expected to be extremely rare.

Identifying Safety Events

Safety events may be elicited at baseline during the NetSCID-5 assessment or spontaneously reported to study staff at any visit following consent. Examples of spontaneously reported (unsolicited) safety events include:

- Receiving an unsolicited remark or complaint from the participant or a friend, family member or other person about the participant's intent to harm themselves.
- Information may be discovered after the participant spontaneously reports a complaint (e.g., plans to attempt suicide).

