When safety events are reported, study staff will obtain as much information as possible about the reported event to complete documentation of the Safety Event Log and will consult with the Study Clinician and Lead Investigators as warranted. Safety event assessment will begin with participant consent and follow-up will continue until resolution, stabilization or study end. All reported safety events will be followed until resolution or stabilization but will cease at the end of the 12-week active window for participants in the study.

Documenting Safety Events

Any safety event that occurs after consent will be documented on the designated Safety Event Log. All safety events will be brought to the attention of the Lead Team and reviewed on the weekly study call.

Suicidal ideation will not be captured as AEs or SAEs but instead will be reported on the Safety Event Log described below.

Suicidal ideation may be reported via the NetSCID-5 assessment at baseline or via spontaneous report from the participant. In the event of suicidal ideation and behavior reporting, participants may need additional and immediate follow-up from the Study Clinician. Refer to the Critical Incident SOP for further details.

Monitoring Safety Events

Quality Assurance (QA) monitors will routinely review study records for any unreported safety events and ensure these events are promptly reported to the Lead Investigators, and to the IRB of record, per IRB reporting requirements. The monitor will document safety related information in the Site Visit Report. Any unreported safety events identified by monitors will be reported as protocol deviations. To ensure timely identification and reporting of future safety events, study staff education, re-training, or another appropriate corrective action plan may be implemented when unreported safety events are discovered. See Module 10 of the study Manual of Operating Procedures for specific guidelines on monitoring processes.

Reporting Safety Events

What to report?	
 This study has no reportable AEs or SAEs. Only safety events (i.e., suicidality and deaths) will be recorded in the Safety Event Log. If required, study staff will report safety events to the IRB of Record in accordance with the IRB’s policies and procedures.

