If information related to the safety event is not completed when it is initially reported or if new information becomes available after the Safety Event Log is submitted, a follow-up report (containing any additional or updated information) must be submitted as soon as possible, but at most within 14 days after the study staff receives the updated information.

The anticipated safety events for this study (i.e., suicidal ideation) are *not* required to be reported to the KPNC IRB unless there is evidence that they are causally related to the research procedures. If a site is ever unsure whether an event should be reported to the IRB, they should discuss with the KPNC IRB.

While unlikely to occur in this low-risk study, unanticipated study-related problems involving risks to subjects or others must be reported via KPNC IRB's Reportable New Information Form, with supporting documentation as soon as possible, but no later than 5 business days of becoming aware of the event and deaths unanticipated and possibly related to the study must be reported within 24 hours (see the study Manual of Operating Procedures for a description of these events and reporting requirements).

All events should be followed up to resolution.

Sponsor's Role in Safety Management Procedures of Safety Events

The Sponsor or designee will not be involved in safety management procedures for this study. The Study Clinician is responsible for reviewing all Safety Events. The Lead Investigators and designees will also be promptly informed of all reported Safety Events, for example via email. The Lead Investigators or designee will report to external parties as required, including the sponsor and IRB of record.

Reporting Safety Events to the Data and Safety Monitoring Board

There will be no DSMB for this study.

Participant Discontinuation Due to a Safety Event

There may be some situations in which a safety event requires that a participant be discontinued from study participation. Participants may be discontinued from the study in the following situation(s):

- Participant's condition has deteriorated during the course of the study:
 - Emergence of psychosis, suicidal ideation, overdose, severe cognitive impairment, dangerous criminal behaviors; or
 - New onset of psychiatric or medical conditions requiring intervention that preclude continued study participation.

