2.0 OVERSIGHT OF CLINICAL RESPONSIBILITIES

A. Site Principal Investigator

The Site PI is responsible for study oversight, including ensuring human research subject protection by designating appropriately qualified, trained research staff and medical clinicians to assess, report, and monitor adverse events.

All reportable Safety Events occurring during the course of the study will be collected, documented, and reported by the investigator or designee to the Protocol.

The occurrence of Safety Events will be assessed as appropriate. All Safety Events will be followed up to resolution as described in Appendix A of the Protocol.

Most reportable Safety Events are required to be reported to the Kaiser IRB within 5 business days of the site staff becoming aware of the event. However, some reportable Safety Events (including death and unauthorized use or disclosure of confidential subject information or KP information) are required to be reported to the Kaiser IRB within 1 business day of site's knowledge of the event (see the study Manual of Operating Procedures for more detailed information).

B. Safety Monitor/Medical Monitor

Since this is a minimal risk study, a Safety Monitor/Medical Monitor will not be appointed. Safety Events will be reported to the Study Clinician and Lead Investigators who will, in turn, report to applicable regulatory bodies, including the IRB of Record.

C. Data and Safety Monitoring Board (DSMB)

Not applicable as there will be no DSMB.

D. Quality Assurance (QA) Monitoring

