- **Risk from mobile sensing:** Participants might experience slight initial discomfort while wearing the smartwatch, such as minor skin irritations. As with any electrical device, the sensors can theoretically cause electric shocks. Electric shocks can be a health concern with certain health conditions (e.g., heart conditions that require a pacemaker). Additionally, participants could have privacy concerns regarding mobile sensing (smartwatch or smartphone).
 - Although slight discomfort is possible from wearing the smartwatch, the smartwatch

has been used in multiple field studies with many participants, and no significant skin irritation has been reported. Therefore, we expect the severity of the discomfort and irritation of wearing the smartwatch to be minimal. If irritation persists to a point where the participant no longer wishes to participate, any irritation is reversible once the participant removes the smartwatch.

- While electrical devices do introduce the risk of electric shocks, the probability of a participant experiencing even minor electrical shocks is negligible. High impedance circuitry is used to limit current flow, even in the case of external events (e.g., through physical breaking of the sensor board or shorting of the battery leads). All sensors in the smartwatch are commonly used in mobile phones and other activity monitors and pose minimal risk to participants. Previous studies with wristband sensors have indicated that after a brief adjustment period, the majority of the participants adjusted to wearing the bands and did not find them to be intrusive or restraining. We expect that the smartwatch, which have precedent of prior use in a research study or have otherwise been designed for everyday wear, will elicit similar acceptability among the participants in this study.
- Regarding privacy concerns, participants' contact information will be linked to their study data via a code. Participants will be informed of their rights to terminate their participation in the study at any time. Participants will also be informed of their rights to remove the smartwatch and/or not carry their smartphone if they so choose, if they do not wish to be tracked.

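### The Safety Event Log is limited to suicidal ideation and death, which conflicts with Appendix B and Section 15.16 and leaves harms attributed to the study outside routine safety review

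*Combined protocol and SAP*

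**What the plan says.** The narrow definition appears in three places.

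- Section 15.16.3: "We will only collect safety events related to suicidal ideation and death".
- Appendix A, Definition of Safety Events: "safety reporting will be limited to reporting suicidal ideation and deaths only". The same paragraph says that "no causally related Adverse Events (AE) or Severe Adverse Events (SAE) are anticipated and will not be captured".
- Appendix A, Reporting Safety Events: "This study has no reportable AEs or SAEs". The log is again confined to suicidality and deaths.

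Other passages assume a wider scope.

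- Appendix B, 2.0 part A, says that reportable Safety Events will be collected, documented and reported. It then singles out for the shortest IRB deadline "some reportable Safety Events (including death and unauthorized use or disclosure of confidential subject information or KP information").
- Section 15.16: "All events that are serious, related and unexpected, or that place subjects at greater risk of harm will be promptly reported to Kaiser IRB". Appendix A carries a near-identical rule. Neither is confined to suicidality and death.
- Section 2.5 offers suicidal ideation only as an example of a safety event, so the list there is open.

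Appendix B, Study Specific Risks, names what the study itself might cause: fatigue, frustration or discomfort from EMA questions; irritation from the watch ("Participants might experience slight initial discomfort while wearing the smartwatch, such as minor skin irritations"); a theoretical electric shock; and privacy concerns from sensing and social media. Section 14.10 plans no safety analysis.

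**The concern.** Staff are told in one place that a disclosure of confidential data is a Safety Event to be documented, and in another that only suicidal ideation and death are. The rule on serious, related events presupposes that such events come to notice and are written down, yet the definition of what is recorded excludes them.

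Two safeguards use the same definition. The weekly review for trends and unusual events (Section 15.16.2) covers safety events. The monitors' check of study records (Appendix A, Monitoring Safety Events) looks for unreported safety events. Whatever the definition leaves out, both leave out.

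The primary objective is feasibility (Section 5.1), and Section 2.4 says the results are meant to inform other studies in people with OUD. As planned, the report could give wear and response rates. It could not give a count of harms or problems that participants or staff attributed to the devices or procedures.

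**Working it through.** The question is one of scope, so no power or sample-size figure is involved. The check takes each kind of event the documents mention and follows it through the record-keeping and reporting steps.

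| Event | In the log definition | Weekly review and QA search | IRB route | Other record |
|---|---|---|---|---|
| Suicidal ideation | Yes | Yes | Yes, if there is evidence of a causal link to study procedures (Appendix A) | NetSCID-5 at baseline |
| Death | Yes | Yes | Yes | Notified to NIDA (15.16.3) |
| Unauthorized disclosure of data | No | No | Yes, within 1 business day (Appendix B, 2.0 part A) | Deviation record, if it is also noncompliance (15.15) |
| Serious or unanticipated device injury | No | No | Yes (15.2, 15.16, Appendix A) | EHR encounter if care was sought, without attribution to the study |
| Skin irritation under correct wear | No | No | None clear | Device-experience question at about week 12 (11.4.1) |
| EMA distress short of suicidality | No | No | None clear | Same question |

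**Rows 3 and 4.** These events are reportable but have no log entry. An IRB report depends on someone recognizing the event. The two routine checks that might catch a missed one do not look for it.

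**Rows 5 and 6.** The route for unanticipated problems (Section 15.2 and Appendix A) does not clearly reach risks that Appendix B already anticipates. A deviation under Section 15.15 is noncompliance, and irritation from wearing the watch as instructed is not noncompliance. The follow-up interview asks about device experience once and is not framed as collection of harms. Under Section 10.3, people who withdraw consent are no longer followed. Appendix B itself foresees that persistent irritation could lead someone to stop participating, so the people most affected may never be asked.

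**Further wording to reconcile.** Section 15.16 requires an event to be serious, related and unexpected. The Appendix A version lists the same terms with commas and ends in an 'or', which can be read as any one of them. Appendix A also lists overdose under discontinuation due to a safety event, after stating that overdoses are not safety events.

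**Exposure.** The active phase is 12 weeks × 7 = 84 days. For 50 to 75 participants (Section 2.3) the planned total is 50 × 84 = 4,200 to 75 × 84 = 6,300 participant-days. Each day asks for at least 18 hours of watch wear and 8 hours of carrying the phone (Section 11.2).

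**The case against.** The best defense is that this is a deliberate choice for a minimal-risk observational study. Appendix A gives the reason for the narrow log, and Section 15.16.1 records that a Protocol Review Board approved the protocol. Appendix B reports no significant skin irritation in multiple field studies, notes that irritation reverses when the watch comes off, and calls the chance of a shock negligible. Participants may skip surveys or remove the watch. Staff contact people after two days without data (Section 8.3), non-engagers are not withdrawn, and poor tolerance would tend to show in the wear and response rates. Operational detail sits in the Manual of Operating Procedures and other procedures that are not part of these documents.

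Much of this stands. It shows that the expected harms are minor, that serious ones have a route, and that people who merely stop using the devices can still be interviewed. It does not resolve the conflict over what a Safety Event is. A low wear rate also does not say whether harm was the reason.

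Three stronger readings are tempting, and the documents do not support them.

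- A reader might infer that study-caused harms are captured nowhere. That is true only of the log. Sections 15.2, 15.15 and 15.16 and both appendices provide IRB or deviation routes.
- A reader might infer two competing deadlines for a breach, because Appendix A sets "no later than 5 business days of becoming aware of the event" for unanticipated problems and Appendix B sets 1 business day. Appendix B states 5 business days as the general rule and 1 as the exception for events such as disclosure. The 5 days in Appendix A is consistent with that general rule and does not mention breaches.
- A reader might infer that the log holds only events expected to be unrelated to the study. Appendix B opens its study-specific risks with suicidal ideation, so the log does cover one of them.

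**Conclusion.** The point holds as a conflict of definitions with a limited practical gap. Section 15.16.3 and Appendix A confine collection and the log to suicidal ideation and death. Appendix B counts data disclosure as a Safety Event to be documented, and Section 15.16 with its Appendix A counterpart requires prompt reporting of serious, related events that the log does not record. Of the six kinds of event tabulated, two are in the log, two are reportable to the IRB but outside the log and the routine checks, and two have no clear record beyond one late question.

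Expected severity is low, and neither the primary outcomes nor their analysis are affected. The correction is still worth making, because staff have conflicting instructions and the feasibility report would lack a count of harms attributed to the study.

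This assumes that the Manual of Operating Procedures, the Critical Incident SOP and the local safety plan do not already define such a record. If one does, the remaining task is to cite it and align the protocol's definitions with it.

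**What to change.** 1. Use one definition of Safety Event in Section 15.16.3, Appendix A (definition and reporting table) and Appendix B 2.0 part A. Align Section 2.5 and the two versions of the rule on serious, related and unexpected events with it.
2. In Appendix A, delete the statement that causally related events are not recorded.
3. Add one category to the Safety Event Log: any harm or problem that a participant or staff member attributes to study procedures or devices, including skin or electrical injury, distress from EMA questions, and loss or disclosure of data. The existing weekly review and QA check then cover it.
4. Report the count descriptively with the feasibility results.

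The cost is one log row, some wording changes and a few minor entries. No new visits or staff are needed, and the IRB deadline for a breach stays as Appendix B states it.
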